### **7 STUDY ASSESSMENTS**

Every effort should be made to ensure that the protocol-required tests and procedures are completed as described. However, it is anticipated that there may be circumstances, outside of the control of the Investigator that may make it unfeasible to perform the test. In these cases, the Investigator will take all steps necessary to ensure the safety and well-being of the subject. When a protocol-required test cannot be performed, the Investigator will document the reason for this and any corrective and preventive actions that he or she has taken to ensure that normal processes are adhered to as soon as possible.

#### **7.1 General Assessments**

##### **7.1.1 Participant Consent**

Before the initiation of any study procedures, all potential subjects or their legal representative must be fully informed of the risks and potential benefits of trial participation and demonstrate understanding. An informed consent document must be signed and dated by the participant or their legal representative indicating that they understand the risks and consent to participation and treatment on the study. The Principal Investigator or their appropriately trained and delegated study personnel conducting the informed consent discussion must also sign and date the document. A copy of the signed document should be provided to the subject.

Procedures, laboratory tests, or imaging performed as part of the standard of care prior to subject consent may contribute to the assessment of eligibility and/or screening procedures if performed during the screening period.

##### **7.1.2 Medical History**

The investigator or appropriately trained and delegated study personnel will collect medical history to the extent that supports the assessment of eligibility. The medical history will include any active conditions and any conditions deemed to be clinically significant by the treating investigator. The use of symptom terms should be discouraged; if possible, terms describing the principal condition or syndrome should be used.

When collecting medical history specific attention should be given to:

- History of Coronary Artery Disease
- Alcohol history (never used alcohol, current alcohol user, former alcohol user)
- Smoking history (never smoked, current smoker, former smoker)
- Pack years (average number of packs per day and number of years smoked)
- Current employment status (employed, retired, student, unknown, other)
- Insurance status (private insurance, Medicare, Medicaid, VA, military, not insured, self-pay, unknown, other)
- Substance use history; including prior history with psychedelics including ketamine.

### **7.1.3 Cancer History**

The oncologic history of the malignancy under study will be collected at the screening visit and will include prior regimens (duration of therapy, the best response on therapy, date of discontinuation, and reason for discontinuation), surgery, radiation therapy, and sequence.

### **7.1.4 Concomitant Medications**

All medications currently being used by a study participant, regularly or as needed, must be reviewed and documented by the investigator or qualified designee. Specific attention should be given to medications with a protocol required washout as described in the exclusion criteria and any medication taken 28 days prior to ketamine. Refer to Section 6.5.1 for prohibited medications.

During protocol therapy, any medications taken by the patient or used to treat an adverse event will be documented in the subject's research chart and the corresponding eCRF. If a new anticancer therapy is initiated during study follow-up, the new therapy should also be recorded in the subject's research chart and corresponding eCRF...

## **7.2 Safety Assessments**

### **7.2.1 Physical Examinations and Vital Signs**

Subjects will have physical examinations to include major body systems, vital signs (blood pressure, heart rate, respiration rate, and pulse oximetry), assessment of ECOG performance status (see Appendix 1), and weight at the time points described in the Schedule of Events. If necessary to facilitate scheduling, the physical exam may occur one day before study treatment.

### **7.2.2 Adverse Events**

Adverse events experienced during trial participation will be collected per the Schedule of Events and Adverse Events Section. Each study participant will be questioned about the occurrence of adverse events in a non-leading manner.

### 7.2.3 Laboratory Assessments

Samples for all laboratory assessments will be drawn at the time points indicated in the Study Calendar and when clinically indicated. Laboratory tests may be performed up to 3 days before the scheduled clinic visit. All safety laboratory analyses will be performed by the local laboratory for each study center. When applicable, all safety laboratory assessments must be reviewed by the treating investigator before study drug administration. When applicable, results from the pregnancy test must also be available for review before dosing.

**Table 1: Laboratory Assessments**

Laboratory Assessments	
Chemistry	
 
• Complete Metabolic Panel           
 
○ Sodium
 
○ Potassium
 
○ Chloride
 
○ Carbon Dioxide
 
○ Alkaline Phosphatase
 
○ Aspartate Aminotransferase
 
○ Alanine Aminotransferase
 
○ Urea Nitrogen
 
○ Glucose
 
○ Creatinine
 
○ Calcium
 
○ Protein
 
○ Albumin
 
○ Bilirubin
 
 
 

Urine Drug Test	
 
• Drug abuse panel
 
• THC urine screen
 

Pregnancy	
 
• Beta-hCG Qualitative Urine or Serum
 

### 7.2.4 12-Lead Electrocardiograms

A standard 12-lead (with a 10-second rhythm strip) tracing will be used for all ECGs. All subjects will require a single 12-lead ECG measurement according to the Schedule of Events only if clinically indicated. The parameters to be recorded are QT, QTc, PR, and QRS. All ECGs should be conducted pre-dose and Fridericia's formula will be used for all QT correction calculations.

If at any time the QTcF > 500 ms, a triplicate ECG will be performed with tracings approximately one-minute apart.

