## ABREVIATIONS

Abbreviation	Definition/Explanation
ACI	As clinically indicated
AE	Adverse event
ALT	Alanine aminotransferase
ASCO	American Society of Clinical Oncology
AST	Aspartate aminotransferase
AV	Atrioventricular
BCVA	Best-corrected distance visual acuity
BICR	Blinded Independent Central Review
β-HCG	Beta-human chorionic gonadotropin
BID	Twice daily
BMI	Body mass index
BP	Blood pressure
BUN	Blood urea nitrogen
CBC	Complete blood count
CFR	Code of Federal Regulations
CHF	Congestive heart failure
CI	Confidence interval
CLIA	Clinical Laboratory Improvement Amendments
CL cr	Creatinine clearance
C max	Maximum observed concentration
C min	Trough observed concentration
CMP	Comprehensive metabolic panel
CNS	Central nervous system
CR	Complete response
CRF	Case report form
CT	Computed tomography
CTCAE	Common Toxicity Criteria for Adverse Events
ctDNA	Circulating tumor DNA
CYP	Cytochrome P450
CQ	Chloroquine

Abbreviation	Definition/Explanation
DILI	Drug-Induced Liver Injury
DoR	Duration of Response
DSMB	Data Safety Monitoring Board
ECOG	Eastern Cooperative Oncology Group
eCRF	Electronic case report form
ECG	Electrocardiogram
Eg	Exempli Gratia (for example)
FDA	Food and Drug Administration
GCP	Good Clinical Practice
GFR	Glomerular filtration rate
GGT	Gamma-glutamyltransferase
GI	Gastrointestinal
GMP	Good Manufacturing Practice
HBsAg	Hepatitis B surface antigen
HBV	Hepatitis B virus
HCV	Hepatitis C virus
HIV	Human immunodeficiency virus
HR	Heart rate
i.e.	Id est (that is)
IEC	Independent ethics committee
IND	Investigational New Drug
INR	International normalized ratio
IRB	Institutional review board
LDH	Lactate dehydrogenase
MRI	Magnetic resonance imaging
NIH	National Institute of Health
KAP	Ketamine-assisted Psychotherapy
PD	Pharmacodynamic(s)
PDAC	Pancreatic Ductal Adenocarcinoma
PFS	Progression-Free Survival
PK	Pharmacokinetic(s)

---

Abbreviation	Definition/Explanation
PO	Per os (administered by mouth)
PR	Partial response
PT	Prothrombin time
PTT	Partial thromboplastin time
QTc	QT interval corrected
QTcF	QT interval corrected using Fredericia equation
RBC	Red blood cell
RP2D	Recommended Phase 2 Dose
SAE	Serious adverse event
SD	Stable disease
SD-OCT	Spectral-domain ocular coherence tomography
T 1/2	Terminal elimination half-life
TdP	Torsades de Pointes
T max	Time of maximum observed concentration
ULN	The upper limit of normal
VF	Visual field
WBC	White blood cell

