	
 
• Screen positivity for existential distress on the EDS, defined as scoring <math>\geq 3</math> on any of the 10 component domains, or a total score <math>\geq 6</math>
 
• ECOG Performance Status <math>\leq 2</math>.
 
 
Key Exclusion Criteria:
 
 
• Personal history or first- or second-degree relatives with schizophrenia, bipolar affective disorder, delusional disorder, schizoaffective disorder, psychosis, or other psychotic spectrum illness.
 
• Currently meeting DSM-5 criteria for Dissociative Disorder, or other psychiatric conditions judged to be incompatible with the establishment of rapport or safe exposure to ketamine.
 
• Currently meeting DSM-5 criteria for Cluster B Personality Disorder.
 
• Severe depression requiring immediate standard-of-care treatment (e.g., hospitalization).
 
• Suicidal ideation over the past month as assessed as a yes to question 3, 4, or 5 on the Columbia-Suicide Severity Rating Scale, Suicidal Ideation section
 
• Cancer with known CNS involvement, previously treated brain metastasis, or other major CNS disease.            Current or history within the last two years of meeting DSM-V criteria of substance use disorder (excluding caffeine and nicotine). Current substance use disorders may be identified through the drug urine screening test.
 
• Congestive heart failure, including all New York Heart Association Classes.
 
• Angina pectoris, cardiac hypertrophy, cardiac ischemia, myocardial infarction
 
• Uncontrolled hypertension at the time of enrollment (BP<math>>140</math> systolic or 90 diastolic), coronary artery disease, artificial heart valve
 
• Prolonged or congenital long QT syndrome (<math>>450</math> ms), serious cardiac arrhythmias, tachycardia, a clinically significant screening ECG abnormality
 
• History of hypersensitivity to ketamine
 
• Receiving ketamine treatments for psychiatric condition within the past 6 months
 
• Seizure disorder
 
• Moderate to severe dementia
 
• History of significant traumatic brain injury
 
• Requires the use of supplemental oxygen.
 

--	---

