## 5 STUDY POPULATION

Potential study participants must meet all inclusion criteria and no exclusion criteria to be deemed eligible for trial participation. To ensure subject safety, all subjects must be deemed eligible at the time of study registration and must continue to meet eligibility criteria up to ketamine dosing. This eligibility checklist is used to determine subject eligibility and will be filed with the enrolling investigator's signature in the subject research chart.

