## 5.2 Exclusion Criteria

1.  Received ketamine treatments for a psychiatric condition within 6 months of enrollment.
2.  Personal history or first- or second-degree relatives with schizophrenia, bipolar affective disorder, delusional disorder, schizoaffective disorder, psychosis, or other psychotic spectrum illness.
3.  Currently meeting DSM-5 criteria for Dissociative Disorder, or other psychiatric conditions judged to be incompatible with the establishment of rapport or safe exposure to ketamine.
4.  Currently meeting DSM-5 criteria for Cluster B Personality Disorder.
5.  Severe depression requiring immediate standard-of-care treatment (e.g., hospitalization).
6.  Suicidal ideation over the past month as assessed as a yes to question 3, 4, or 5 on the Columbia-Suicide Severity Rating Scale, Suicidal Ideation section
7.  Cancer with known CNS involvement, previously treated brain metastasis, or other major CNS disease.
8.  Current or history within the last two years of meeting DSM-V criteria of substance use disorder (excluding caffeine and nicotine). Current substance use disorders may be identified through the drug urine screening test.
9.  Current evidence of uncontrolled, significant intercurrent illness including, but not limited to, the following conditions:
  - Cardiovascular disorders:
    - Any grade congestive heart failure, unstable angina pectoris, serious cardiac arrhythmias including tachycardia, or clinically significant screening ECG abnormalities.
    - Cardiac hypertrophy or artificial heart valve.
    - Stroke (including transient ischemic attack [TIA]), myocardial infarction (MI), or other ischemic events, or thromboembolic event (eg, deep venous thrombosis, pulmonary embolism), and/or significant coronary artery disease within 3 months before the first dose.
    - QTc prolongation defined as a QTcF > 450 ms.
    - Known congenital long QT.
    - Uncontrolled hypertension defined as  $\geq 140/90$  as assessed from the mean of three consecutive blood pressure measurements taken over 10 minutes.

- Seizure disorder
- Moderate to severe dementia
- History of significant traumatic brain injury
- Requires the use of supplemental oxygen.
- Renal insufficiency as defined as creatinine clearance < 40 mL/min calculated by Cockcroft-Gault formula

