## 5.3 Registration

Subjects must complete all screening procedures and meet all of the eligibility requirements before registration. Study-related screening procedures can only begin once the subject has signed the consent form. Subjects must not begin protocol treatment prior to registration.

Treatment should start as soon as logistically possible after registration.

To register eligible subjects on study, complete a Clinical Trials Office Subject Registration Form and submit to [[contact]](mailto:[contact]).

For sites outside of Huntsman Cancer Institute, submit registration forms to [[contact]](mailto:[contact])

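### Section 7.2.4 makes the 12-lead ECG conditional on clinical indication, while the Schedule of Events marks it for every subject at screening and exclusion 9 cannot be applied without it

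*Combined protocol and SAP*

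**What the plan says.** Section 7.2.4, the section devoted to ECGs, sets the requirement in one sentence: "All subjects will require a single 12-lead ECG measurement according to the Schedule of Events only if clinically indicated". It then adds: "All ECGs should be conducted pre-dose and Fridericia's formula will be used for all QT correction calculations". It closes with a rule that a QTcF above 500 ms, whenever it is found, triggers a triplicate recording.

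The ECG row of the Schedule of Events (Section 1.4) carries an unconditional X in the Screening column and ACI under the ketamine sessions. The abbreviation list defines ACI as "As clinically indicated".

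Exclusion 9 in Section 5.2 lists "QTc prolongation defined as a QTcF > 450 ms" and also "serious cardiac arrhythmias including tachycardia, or clinically significant screening ECG abnormalities". The synopsis (Section 1.1) has a matching exclusion: a QT limit of 450 ms together with "serious cardiac arrhythmias, tachycardia, a clinically significant screening ECG abnormality".

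Two general rules govern entry. Section 5.3 says: "Subjects must complete all screening procedures and meet all of the eligibility requirements before registration". Section 5 says that subjects "must continue to meet eligibility criteria up to ketamine dosing" and provides for a signed eligibility checklist.

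**The concern.** The Schedule attaches the as-indicated condition only to ECGs at the ketamine sessions. Section 7.2.4 attaches it to the one ECG that it requires at all. Its sentence also pulls against itself: it covers all subjects and points to the Schedule, then makes the ECG depend on an indication.

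This matters because the ECG is the only listed procedure that yields a QTcF. A patient with a prolonged QTcF may have no symptom or history that would count as a clinical indication. If the ECG is omitted for that reason, the 450 ms exclusion and the screening-abnormality exclusion are not tested before the patient is dosed. The protocol classes the trial as high risk (Section 8.4), so whether a stated cardiac exclusion is checked should not depend on which section a coordinator opens.

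The timing sentence raises a second, smaller problem. An indication for an ECG at a ketamine session may well arise after the injection, and the text does not say how its pre-dose wording applies then.

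**Working it through.** No sample size, power or error rate is involved, and the plan states no figure to reproduce. The check is a side-by-side reading.

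**Step 1. Is an ECG required of every subject at screening?**

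| Place | Answer |
|---|---|
| Schedule of Events, Screening column | Yes, without condition |
| Schedule of Events, ketamine sessions | As clinically indicated |
| Section 7.2.4 | All subjects, per the Schedule, but only if clinically indicated |
| Exclusion 9 and synopsis | Not stated, but both refer to screening ECG abnormalities and set a 450 ms QT limit, so a tracing is presupposed |

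The Schedule, exclusion 9 and the synopsis fit together. The condition in Section 7.2.4 fits none of them.

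**Step 2. Would another step catch an omitted ECG?**

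- Section 5.3 requires all screening procedures to be complete before registration. That catches the omission if the Schedule defines those procedures. It may not if staff take Section 7.2.4 to define the ECG procedure and see no indication.
- Section 5 requires eligibility to hold up to dosing, but it names no procedure for establishing QTcF.
- Section 6.2.2 lists a psychiatric evaluation, a medical history review and a physical exam before the first visit. Immediately before each dose it lists allergy, fasting and medication checks, blood pressure, oxygen saturation, respirations, alertness, movement and an escort. No ECG appears in either list.

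The safeguards are real, but they depend on the Schedule being read as governing. No passage says which text prevails.

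**Step 3. Does the pre-dose wording conflict with anything?**

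- Screening ECG: no conflict, since screening precedes dosing.
- As-indicated ECGs at sessions: poor fit. The protocol checks cardiovascular measures 40 minutes and 2 hours after the injection (Schedule footnote 6, Section 6.2.4), so an indication can arise after the dose.
- QTcF > 500 ms repeat rule: poor fit. It applies at any time, while the sentence before it asks for every ECG to be pre-dose.

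**Step 4. Size.**

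- Screening ECGs under the Schedule: one per person screened. With 12 enrolled (Section 5.5.1) that is at least 12 × 1 = 12, and more once screen failures (Section 5.4) and replaced subjects (Section 9.2) are counted.
- Screening ECGs required regardless of indication under a literal reading of Section 7.2.4: 0.
- Planned doses that follow from those enrolments: at most 12 × 3 = 36.

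These are bounds from a literal reading, not expected effects. The number dosed with an untested QTcF above 450 ms lies between 0 and 12. The documents give neither the frequency of such values nor the chance that an ECG would be omitted, so the range cannot be narrowed.

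**The case against.** The strongest reply is that Section 7.2.4 does not set eligibility. Its sentence begins with all subjects and refers to the Schedule, so the likely intent was a screening ECG for everyone and further ECGs as indicated. Exclusion 9 applies whatever Section 7.2.4 says, Sections 5 and 5.3 enforce it, and a checklist is signed. Section 7.1.1 also lets standard-of-care procedures done in the screening period count, so a tracing may exist even where the study does not demand one. Much of this stands: it makes an omission less likely. It does not remove the conflict, because the intended meaning has to be inferred and no rule of precedence is given.

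A reader might infer several stronger points that the documents do not support.

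- *Patients with QTcF above 450 ms will be enrolled and dosed.* That would mean setting aside the Schedule, exclusion 9 and the registration rule on the strength of one clause. It is possible, not predicted.
- *The ECG is the only objective cardiac screen.* Screening also includes blood pressure, heart rate, pulse oximetry and a physical exam, and exclusion 9 has a blood pressure limit based on three readings. The ECG is the only listed source of QTcF, which is a narrower statement.
- *Post-dose ECGs are forbidden.* The text says that ECGs should be pre-dose. It does not prohibit others, and the Schedule and the repeat rule both leave room for them. Emergency response and supportive care are covered in Sections 6.2.4 and 6.5.
- *The safety endpoint is compromised.* That endpoint is a descriptive summary of adverse events (Sections 2.2.1 and 9.4.1), and no ECG variable is analysed.

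**Conclusion.** The concern holds as an internal inconsistency that bears on patient safety. Section 7.2.4, as worded, contradicts the Schedule on whether the screening ECG is conditional, and it leaves open a route by which the QTcF and screening-abnormality exclusions could go untested. Its pre-dose wording also fits poorly with the session ECGs and with its own repeat rule.

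The conflict covers everyone screened. Its practical effect depends on staff treating Section 7.2.4 as the governing text, and the documents neither establish nor rule that out. The trial runs at a single center (Section 5.5.2), which limits variation in practice but does not settle which passage applies. Confidence is high in the conflict of wording and much lower in any particular consequence for a patient.

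**What to change.** Amend Section 7.2.4 so that both its ECG requirement and its timing wording agree with the Schedule of Events and exclusion 9. The sponsor and investigator decide which rule governs. Section 7.2.4, the Schedule and exclusion 9 must then state the same one, with the synopsis kept in line. The amended text should make clear to which ECGs the as-indicated condition and the pre-dose wording each apply, and how the QTcF > 500 ms repeat rule relates to that timing.

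The cost is about two sentences in an amendment, with the IRB review that Section 10.4 requires. If the passages are reconciled to the Schedule as it stands, no procedure is added. If they are reconciled the other way, the Schedule, exclusion 9 and the synopsis would need rewriting too, and Section 8.4 calls for DSMC review of any amendment that increases risk.

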## 7.3 Patient Reported Outcomes

The response to study therapy will be assessed utilizing the Existential Distress Scale (EDS), Quick Inventory of Depressive Symptomatology (QIDS-SR-16), Patient Health, Columbia-Suicide Severity Rating Scale Baseline/Screening and Since Last Visit (C-SSRS), Death

Transcendence Scale (DTS), Functional Assessment of Chronic Illness Therapy - Spiritual Well-Being (FACIT-Sp), , Nondual Awareness Dimensional Assessment (NADA), Mystical Experiences Questionnaire (MEQ-30), Storyline Integrative Assessment, Patient-Reported Experience on Study Therapy, at the time points indicated in the Schedule of Events.

### 7.3.1 Storyline

#### 7.3.1.1 *Psychiatric and Psychology Assessment Components:*

This part of the assessment is a 60-minute program broken into six 10-minute assessments of (i) physical symptoms, (ii) mood & emotion, (iii) cognition, (iv) homeostasis (ie. eating, sleeping, activity patterns) (v) social support and (vi) psychological associations. The program was created, in part, with our collaborator, [name] MD PhD (clinical psychiatrist) from a proven set of psychiatric interview questions and methods for DSM-5 diagnoses of depression, bipolar, anxiety, psychosis, neurocognitive disorders (dementia and delirium), suicidality, addiction, trauma and physical health. This interview uses open-ended questions that evaluate RDoC domains and create a caring and natural interview experience that is non-threatening using “normalization”, “reduction of guilt” and “symptom exaggeration” techniques, as well as providing safety, transparency, education and logical flow. Cognition is assessed, in part, using established clinical tests of cognitive functioning, including tests of (i) orientation (date, day of the week, location), (ii) short-term memory, (iii) long-term memory and recall, (iv) semantic fluency, (v) verbal fluency, (vi) working memory, (vii) attention and (viii) self-initiation. In addition, open-ended questions are included that ask for descriptions of (1) concerns about brain functioning, memory, concentration and fatigue, (2) any noticeable changes in memory or thinking, brain fog, headaches, (3) social interactions and perceived support, and (5) a 1-5-minute story about “something that happened to you this week”. The psychological associations assessment uses open-ended descriptions (“What does this make you think of?”) to capture responses to neutral, positive and negative cues, including Eckman faces (neutral, happy, sad, angry, disgust, surprise, contempt), Open Affective Standardized Image Sets (OASIS) and Affective Norms for English Words (ANEW) with valence, arousal or dominance characteristics predictive of mental illness (ie. death, cruelty, trouble, carefree, good, and praise). Finally, the Storyline assessment includes the standard PHQ-2, GAD-2 and PCL-2 questionnaires of clinical depression, anxiety and trauma symptoms as internal controls for clinical symptomology.

The neurological assessment developed by Storyline is 10 minutes long and is similar to a standard of care neurological exam. It includes questions that test eye movement, facial expression, speech, finger movements, hand movements, cognition and drawing. The material for this assessment is derived from the following leading clinical neurology textbook: “Neurological Examination Made Easy 6th Edition” by Geraint Fuller MD FRCP.

